5.3 SCREEN FAILURES

Screen failures are defined as participants who consent to participate in the clinical trial but are not subsequently randomly assigned to the study intervention or entered in the study. A minimal set of screen failure information is required to ensure transparent reporting of screen failure participants, to meet the Consolidated Standards of Reporting Trials (CONSORT) publishing requirements and to respond to queries from regulatory authorities. Minimal information includes demography, screen failure details, eligibility criteria, and any serious adverse event (SAE).

Individuals who do not meet the criteria for participation in this trial (screen failure) because of OSDI score may be rescreened. Rescreened participants should be assigned the same participant number as for the initial screening.

5.4 STRATEGIES FOR RECRUITMENT AND RETENTION

Anticipate 25 screenings for 12 enrolled subjects.

- *One site in the US.*
- *Source of participants will be outpatient clinics and general public*
- *Potential participants will be identified and approached by chart review, during regular dry eye clinic visits and self-identified by general dry eye study signs within our clinics*

6 STUDY INTERVENTION

The study intervention is H.P. Acthar Gel (repository corticotropin injection) an adrenocorticotropic hormone (ACTH) analogue used on label as currently approved by the FDA for ocular inflammation. *This study will be used to gather data specifically about the efficacy and safety of use of Acthar in moderate to severe dry eye.*

6.1 STUDY INTERVENTION(S) ADMINISTRATION

6.1.1 STUDY INTERVENTION DESCRIPTION

There is no control, only study intervention with H.P. Acthar gel used subcutaneously 80 IU 2-3 times weekly. The drug is currently approved for all ocular inflammation and will be studied in this investigation specifically for moderate to severe dry eye disease.

6.1.2 DOSING AND ADMINISTRATION

Each participant will be started at 80 IU subcutaneously 2-3 weekly and the dosing increased to up to three times weekly at the discretion of the primary investigator. The dosing will remain consistent unless the investigator decides to reduce or escalate the dosing at the one month mark. The dosing may be stopped altogether and the subject followed only for safety in the event of uncontrolled hypertension, blood sugar, glaucoma or other serious adverse events in the opinion of the investigator. The dosing of study drug will continue for 12 weeks.

Missed or delayed doses should be taken as soon as realized unless it would result in two doses being given at once, in which case the investigator should be contacted for a modified dosing schedule.

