1 PROTOCOL SUMMARY

1.1 SYNOPSIS

Title:	A Phase 4 Study to Assess the Clinical Efficacy of H.P. Acthar Gel 80 U/ml to Improve the Signs and Symptoms in Subjects with Dry Eye Disease
Study Description:	This study will test the efficacy of a systemic intervention and adrenocorticotropin injection for severe dry eye unrelieved by traditional dry eye treatments.
Objectives:	The primary objective of the study is to investigate the safety and efficacy of H.P. Acthar gel injections in subjects who have a documental clinical diagnosis of dry eye disease. Secondary objective is to demonstrate safety for use of Acthar H.P. Gel in dry eye subjects.
Endpoints:	Primary Endpoint: Improvement of patient comfort over the length of the study using a validated dry eye comfort questionnaire, OSDI and improvement of spk in cornea over study treatment period Secondary Endpoints: conjunctival staining with lissamine green
Study Population:	12 study subjects 18-85 will be enrolled with male or female in the Nashville, TN area who are generally healthy but have persistent signs and symptoms of dry eye diseases after treatment with traditional dry eye treatments including but not limited to: IPL, cyclosporing, lifitegrast, loteprednol, artificial tears and warm compresses
Phase:	4

Description of *Single site study in Nashville, TN and surrounding areas.*

Sites/Facilities Enrolling

Participants:

Description of Study *Acthar is an adrenocorticotropic hormone given subcutaneously twice*

Intervention: *weekly.*

[figure not shown]
Study Duration: *6 months*

Participant Duration: *12 weeks*

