2.3 RISK/BENEFIT ASSESSMENT

2.3.1 KNOWN POTENTIAL RISKS

Known risks of Acthar use include
Infections
Cushing's syndrome
High blood pressure
Bleeding stomach ulcers
Irritability
Depression
Insomnia
Mood swings
Loss of diabetic control
Cataracts
Glaucoma
Allergy to acthar
Long term use can affect children's growth and development
Osteoporosis
Birth defects

The most common side effects are

Increased blood sugar

Increased blood pressure

Fluid retention

Changes in appetite

Weight gain

Cardiac hypertrophy

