3 OBJECTIVES AND ENDPOINTS

OBJECTIVES	ENDPOINTS	JUSTIFICATION FOR ENDPOINTS
Primary		
The primary objective is the efficacy of H.P. Acthar gel injections in subjects with documented moderate to severe dry eye disease who have failed traditional therapies.	The primary endpoint(s) are improvement in comfort over the course of the trial with a validated dry eye comfort questionnaire, OSDI and improvement in the number of corneal spk using fluorescein stain over the course of the trial.	Both endpoints have been validated in recent dry eye approvals (lifitegrast).
Secondary		
The secondary objective is improvement in conjunctival staining with lissamine green and demonstration of safety of use of in dry eye subjects.	Conjunctival staining with lissamine green is another method of measuring ocular surface inflammation and safety will be measured by collecting intraocular pressure, assessing AEs, slit lamp biomicroscopy, BCVA and dilated ophthalmoscopy	Lissamine green staining has also been used in recent approvals (lifitegrast) and safety of adrenocorticotrophic stimulators must measure common side effects of steroid like glaucoma, cataract and potential change in vision.
.	.	

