7 STUDY INTERVENTION DISCONTINUATION AND PARTICIPANT DISCONTINUATION/WITHDRAWAL

7.1 DISCONTINUATION OF STUDY INTERVENTION

Discontinuation during study does not mean discontinuation from the study, and remaining study procedures should be completed as indicated by the study protocol. If a clinically significant finding is

identified (including, but not limited to changes from baseline) after enrollment, the investigator or qualified designee will determine if any change in participant management is needed. Any new clinically relevant finding will be reported as an adverse event (AE).

The data to be collected at the time of study intervention discontinuation will include the following:

- Subject rated assessment of eye dryness, use of concomitant medications since last visit, occurrence of AEs since last visit, unused investigational product will be collected, BCVA, slit lamp biomicroscopy, iop, dilated fundus exam and pregnancy test for women of childbearing potential.

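### Dosing may be stopped for uncontrolled blood pressure or blood sugar, but neither is scheduled to be measured, so an untreated symptomless rise has no planned check and no baseline value

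*Protocol*

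**What the plan says.** The treatment is "H.P. Acthar gel used subcutaneously 80 IU 2-3 times weekly", self-injected for 12 weeks (Protocol 4.3, 6.1.1, 6.1.2). Section 6.1.2 contains two dosing decisions that depend on the patient's systemic state. One is stopping: "The dosing may be stopped altogether and the subject followed only for safety in the event of uncontrolled hypertension, blood sugar, glaucoma", with other serious adverse events added and the judgement left to the investigator. The other is adjustment: "The dosing will remain consistent unless the investigator decides to reduce or escalate the dosing at the one month mark".

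Section 2.3.1 puts "Increased blood sugar" and "Increased blood pressure" first in its list of the most frequent side effects. It separately lists high blood pressure and loss of diabetic control as known risks.

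The Synopsis (1.1) states: "Secondary objective is to demonstrate safety for use of Acthar H.P. Gel in dry eye subjects". The endpoint column of Section 3 says that "safety will be measured by collecting intraocular pressure, assessing AEs, slit lamp biomicroscopy, BCVA and dilated ophthalmoscopy". When study drug is discontinued, Section 7.1 asks for a dryness rating, concomitant medications and adverse events, and then: "unused investigational product will be collected, BCVA, slit lamp biomicroscopy, iop, dilated fundus exam and pregnancy test for women of childbearing potential".

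**The concern.** The protocol names three specific conditions for stopping treatment. Glaucoma has a scheduled measurement. Hypertension and blood sugar do not, although the protocol itself counts rises in both among the drug's commonest effects.

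Both can rise without symptoms. A patient who feels well, takes no treatment for either and is not tested elsewhere could have such a rise and complete the trial exactly as written without its being seen. The investigator could then neither stop dosing for it nor weigh it before increasing the dose. With no control arm, a measured baseline is the only comparison available within the study, and for these two effects there would be none. The safety results on them would rest on reported events alone.

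**Working it through.** The plan gives no figure to reproduce. The check is a reading of every place where a measurement could be scheduled, followed by simple dose and cost arithmetic.

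1. **Schedule of Activities (1.3).** Fifteen rows have a readable label: consent, demographics, medical history, randomization, study intervention, concomitant medication, BCVA, slit lamp, IOP, fluorescein stain, lissamine stain, Schirmer, dilated ophthalmoscopy, training and dispensing. Blood pressure, vital signs, glucose or laboratory tests among them: 0 of 15. Two more marked rows have no usable label: one is blank and one shows only a stray character. The schedule alone is therefore not conclusive.

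2. **Procedures written out in words.** These do not depend on the damaged table.
   - Section 3, safety endpoints: ocular measures plus adverse events.
   - Section 7.1, discontinuation data: dryness rating, medications, adverse events, ocular examinations, pregnancy test.
   - Section 8.1, visit procedures: the only body-fluid test is a urine pregnancy test.
   - Section 8.2, safety assessments: BCVA, slit lamp, IOP, dilated ophthalmoscopy and adverse events.
   - Sections 9.1, 9.4.3 and 9.4.4 and the SAP: no blood pressure or glucose variable.

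3. **The three named stopping conditions compared.**

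| Condition in 6.1.2 | Adverse event questioning | Scheduled measurement |
|---|---|---|
| Glaucoma | yes | IOP in 5 of 5 displayed columns, plus optic nerve assessment |
| Hypertension | yes | none found |
| Blood sugar | yes | none found |

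4. **Dose at stake.** Twice weekly: 2 × 80 = 160 IU per week. Three times weekly: 3 × 80 = 240 IU per week. Ratio 240/160 = 1.5, a 50% increase. Over 12 weeks, 24 to 36 injections, or 24 × 80 = 1,920 IU to 36 × 80 = 2,880 IU. A patient raised at week 4 receives 4 × 2 + 8 × 3 = 32 injections, or 2,560 IU. The 50% step applies only to patients started twice weekly; 6.1.2 also allows a start at three. These figures describe exposure, not the size of the gap.

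5. **The one-month decision.** The displayed columns are Screening and Days 1, 7, 14 and 84, with no one-month column. The last column is numbered Visit 13, and 84/7 + 1 = 13, so the numbering fits weekly visits that are not displayed. The documents do not list them.

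6. **Readings needed.** One pre-dose reading plus Days 7, 14 and 84: 12 patients × 4 = 48 pairs. With a one-month visit: 12 × 5 = 60. Screening plus 13 numbered visits: 12 × 14 = 168. At an assumed 5 minutes per pair, 48 × 5 = 240 minutes (4 hours) and 168 × 5 = 840 minutes (14 hours). Replacement patients and early-discontinuation readings would add to this.

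**The case against.** The strongest reply is that the protocol is not blind to these effects. The coordinator asks about adverse events at every visit (8.3.4). Medical history and medication review, reaching back six months before screening (8.1), would show known disease and a change in its treatment. Exclusion 10 lets the investigator keep out a patient with an uncontrolled condition. Section 7.2 permits withdrawal for a laboratory abnormality, 10.1.9.1 mentions laboratory data on the case report form, and 10.1.6 sets up a DSMB whose charter will define the data it needs. The stopping provision is discretionary, not a numeric trigger. Section 3 also gives a reason for its ocular focus, and this is a 12-patient uncontrolled pilot of a drug that the protocol describes as used on label.

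Much of this stands. A reader might infer that the study cannot detect hypertension or raised blood sugar at all, or that the stopping provision cannot be used. The documents do not support that: symptomatic, treated or externally found problems can surface, and nothing prevents the investigator from taking a reading. What remains is narrower. The laboratory wording names no test. Exclusion 10 rests on judgement and leaves no measured baseline. The DSMB need meet only twice a year in a six-month study, and no such readings are scheduled for it to review. None of these requires a value for a patient who feels well.

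The unlabelled schedule rows leave some doubt about the table, but a lost label would not explain why four written procedure lists all omit both measurements.

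**Conclusion.** The point holds for the untreated, symptomless rise. Such a rise has no scheduled check and no baseline value, including before a possible 50% dose increase at one month in patients started twice weekly. Scheduled readings found: 0 for blood pressure and 0 for glucose.

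The conclusion rests on the written lists in Sections 3, 7.1, 8.1 and 8.2 being complete, since the schedule has two rows that cannot be read. It does not rest on any assumed rate of symptomless rises; the documents give none.

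Two further inferences should be resisted. The missing one-month column does not show that the dose decision is made without a visit, because the visit numbering suggests visits that are not displayed. Nor does the gap cast doubt on the dryness or staining results, because no efficacy endpoint depends on these readings. The appropriate weight is a cheap improvement to patient safety and to the safety data.

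**What to change.** Add a seated blood pressure and a glucose meter reading, recorded as fasting or non-fasting, at screening or baseline, at each existing visit and at treatment discontinuation. Require both before any dose increase at one month, and tie that requirement to whichever visit or contact makes the decision, since the displayed schedule does not show one. Enter the readings in the Schedule of Activities, 7.1 and 8.2. Have the study clinicians write action levels into 6.1.2 before enrolment: when to repeat, when to refer, and when to hold or not raise the dose.

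The cost is a short amendment, a few minutes and a finger-stick per visit, and follow-up of abnormal readings. The total depends on the true number of visits. If there is no one-month visit, creating one costs more than the five minutes assumed per reading.

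If the readings are not collected, limit the safety objective in 1.1 and in the objective column of Section 3 to ocular safety and reported adverse events. That would agree with the Section 3 endpoint column taken together with 9.4.4. Section 9.1 alone is not enough as a reference, because its safety outcomes are ocular and do not mention adverse events. This alternative costs only wording, but it leaves the patient-safety gap open.

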6.2 PREPARATION/HANDLING/STORAGE/ACCOUNTABILITY

6.2.1 ACQUISITION AND ACCOUNTABILITY

Study drug will be provided by Mallinkrodt and shipped to the investigative site from Mallinkrodt. It will be dispensed to the subject at the time of enrollment by the study coordinator. Unused or expired study drug will be returned to Mallinkrodt.

6.2.2 FORMULATION, APPEARANCE, PACKAGING, AND LABELING

Study drug formulation, appearance, packaging, and labeling will be as normally supplied by the manufacturer, Mallinkrodt Pharmaceuticals. .

6.2.3 PRODUCT STORAGE AND STABILITY

H.P. Acthar gel is stored under refrigeration 2-8 degrees Celsius or 36-46 degrees Fahrenheit. Study drug temperature stability will be monitored with downloadable temperature monitors to ensure safety.

6.2.4 PREPARATION

Study drug should be warmed to room temperature before using. It is supplied in 5 ml multi-dose vials with 80 USP units per ml. Subjects will be instructed to withdraw 1ml.

6.3 MEASURES TO MINIMIZE BIAS: RANDOMIZATION AND BLINDING

All subjects will receive active drug with no control.

6.4 STUDY INTERVENTION COMPLIANCE

Adherence to the protocol will be assessed by verbally discussing with the subject and return of participant drug log.

6.5 CONCOMITANT THERAPY

For this protocol, a prescription medication is defined as a medication that can be prescribed only by a properly authorized/licensed clinician. Medications to be reported in the Case Report Form (CRF) are concomitant prescription medications, over-the-counter medications and supplements.

6.5.1 RESCUE MEDICINE

The study site will not supply rescue medication.

The use of rescue medications is allowable at any time during the study and the date and time of rescue medication administration as well as the name and dosage regimen of the rescue medication must be recorded.

7 STUDY INTERVENTION DISCONTINUATION AND PARTICIPANT DISCONTINUATION/WITHDRAWAL

7.1 DISCONTINUATION OF STUDY INTERVENTION

Discontinuation during study does not mean discontinuation from the study, and remaining study procedures should be completed as indicated by the study protocol. If a clinically significant finding is

identified (including, but not limited to changes from baseline) after enrollment, the investigator or qualified designee will determine if any change in participant management is needed. Any new clinically relevant finding will be reported as an adverse event (AE).

The data to be collected at the time of study intervention discontinuation will include the following:

- Subject rated assessment of eye dryness, use of concomitant medications since last visit, occurrence of AEs since last visit, unused investigational product will be collected, BCVA, slit lamp biomicroscopy, iop, dilated fundus exam and pregnancy test for women of childbearing potential.

7.3 LOST TO FOLLOW-UP

A participant will be considered lost to follow-up if he or she fails to return for 2 scheduled visits and is unable to be contacted by the study site staff.

The following actions must be taken if a participant fails to return to the clinic for a required study visit:

- The site will attempt to contact the participant and reschedule the missed visit within 72 hours and counsel the participant on the importance of maintaining the assigned visit schedule and ascertain if the participant wishes to and/or should continue in the study.
- Before a participant is deemed lost to follow-up, the investigator or designee will make every effort to regain contact with the participant (where possible, 3 telephone calls and, if necessary, a certified letter to the participant's last known mailing address or local equivalent methods). These contact attempts should be documented in the participant's medical record or study file.
- Should the participant continue to be unreachable, he or she will be considered to have withdrawn from the study with a primary reason of lost to follow-up.

8 STUDY ASSESSMENTS AND PROCEDURES

8.1 EFFICACY ASSESSMENTS

List and describe all study procedures and evaluations to be done as part of the study to support the determination of efficacy, as per the primary and secondary objectives outlined in this protocol. Discuss the sequence of events that should occur during the screening process and any decision points regarding participant eligibility. Include the time frame prior to enrollment within which screening procedures/evaluations must be performed (e.g., within 28 days prior to enrollment).

In addition, indicate where appropriate, that procedures/evaluations will be performed by qualified personnel.

- *Once enrolled, initial study visit will occur within one week and can occur on the same day. Study assessments on each study day will occur in this order:*
- ***Subject rated assessment of ocular discomfort by visual analog scale. Subjects will be asked to subjectively rate their eye dryness at Visit 1,2, and 3. Subjects will be instructed to rate eye dryness using the scale below. The total length of the line from “no dryness” to “maximal dryness” is 100 mm. The length of the line between the “no dryness” starting point and the first point at which the subject mark crosses the line will be measured in mm. This assessment is a general assessment of both eyes.***

Instantaneous Evaluation of Eye Dryness

Please place a single line across the line below to indicate the severity of your eye dryness at the present time:

No dryness _____ Maximal dryness _____

- ***Significant non-ocular and significant ocular medical history***
- ***Concomitant medication usage and significant medications taken 6 months prior to screening***
- ***Inclusion/Exclusion criteria***
- ***Urine pregnancy test if required***
- ***BCVA Subjects will be placed at the predetermined mark for ETDRS testing***
- ***. LogMAR will be assessed with ETDRS or modified ETDRS charts and with subjects own corrective lenses or BCVA measured in office whichever is better. Scores are recorded according to ETDRS protocol and right eyes tested first.***
- ***Slit lamp biomicroscopy – 8 mm x 2 mm slit lamp beam will be used right to left and left to right to examine thoroughly the structures of the anterior segment: lids, lashes, conjunctiva, corea, iris, anterior chamber, and lens. Results will be recorded as normal or abnormal. Abnormal findings will be followed by explanation of pathology.***
- ***Corneal fluorescein staining. One drop of tetracaine or properacaine will be applied to the surface of the eye. One drop of Fluress will be applied to the eye, excess blotted and 60 seconds elapsed before the examiner looks for spk. Alternatively, one drop of properacaine or tetracaine can be applied to a fluorescein strip, holding the strip to the inferior fornix for 10***

seconds and allow 120 seconds elapsed prior to examination. Cobalt filter will be used to count discrete and macropunctate staining.

- **Conjunctival lissamine staining. One drop of lissamine green will be applied to each eye, excess blotted, and 60 seconds elapsed before staining is evaluated.**
- **Anesthetized Schirmer. Fold the rounded end of the test strip at the notched area. Instill 1-2 drops of proparacaine or tetracaine and wait 5 minutes. Ask the subject to look up and away from the strip. Place the rounded end of the strip towards the temporal one-third of the lower lid. Repeat procedure on contralateral eye. Instruct the subject to relax and gently close their eyes. Remove strips after 5 minutes and mark with ink the leading and lowest edges of moisture. Measure halfway between the 2 lines and record and the amount of wetting.**
- **IOP measurements will be performed using Goldman applanation tonometry according to the investigators standard protocol. All pressures will be recorded in mm Hg. IOP will be measured at each time point and at the investigator's discretion.**
- **Dilated ophthalmoscopy will occur at the first and last study visit and include assessment of the optic nerve head for pallor and cupping.**
- **Training on study medication dosage will be done by specialists at Mallinkrodt directly with the subject until the subject is deemed by the specialist to be adequately trained and prepared for dosing.**
- **Dispense study medications and temperature log. The study coordinator will dispense both the study medications and the temperature log with instructions on how to begin logging temperatures and when to return the thermometer for downloadable records.**

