5 STUDY POPULATION

5.1 INCLUSION CRITERIA

In order to be eligible to participate in this study, an individual must meet all of the following criteria:

1. Provision of signed and dated informed consent form and HIPPA authorization.
2. Stated willingness to comply with all study procedures and availability for the duration of the study
3. Male or female, aged 18 and older.
4. Diagnosed with moderate to severe dry eye in one or both eyes.
5. History of persistent symptoms despite use of artificial tears and one or more of the following ophthalmic drops: loteprednol, cyclosporine or lifitegrast.
6. At least 40 mm on the ocular discomfort scale.
7. At least 5 spk on one or both corneas.

8. A grade of 1 or greater in the nasal or temporal areas of one or both eyes.
9. Have normal lid anatomy.
10. Ability to take subcutaneous injected medication and be willing to adhere to the study regimen
11. For females of reproductive potential: use of highly effective contraception for at least 1 month prior to screening and agreement to use such a method during study participation and for an additional 4 weeks after the end of Acthar administration
12. For males of reproductive potential: use of condoms or other methods to ensure effective contraception with partner
13. Are postmenopausal (no menstrual cycle for at least one year prior to Visit 1) or have undergone bilateral tubal ligation, hysterectomy, hysterectomy with uni or bilateral oophorectomy, or bilateral oophorectomy.

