9.4.2 ANALYSIS OF THE PRIMARY EFFICACY ENDPOINT(S)

For each primary endpoint:

The improvement of patient comfort as measured by the dry eye comfort questionnaire OSDI defined as the mark listed in mm by the patient describing sensation of dryness. It will be measured at each study visit and reported as an ordinal endpoint. Descriptive statistics will be used for intent to treat patients and safety populations who receive at least one dose of the study drug.

- *The improvement of corneal staining after fluorescein instillation in which discrete superficial punctate stains are counted.. Descriptive statistics will be used for intent to treat patients and safety populations who receive at least one dose of the study drug.*
- *Missing data will be handled by imputation. Outliers will be evaluated by the primary investigator. Subjects who are nonadherent will be referred for re-training and those lost to follow up will be contacted by the study coordinator at least 3 times by phone and ultimately with certified letter if telephone contacts are unsuccessful.*

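### The primary symptom endpoint is named as the OSDI questionnaire but defined as a millimetre mark on a dryness line, and Sections 8.1 and 9.4.2 disagree on whether it is rated at the final visit (Day 84)

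*Protocol*

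**What the plan says.** **Instrument.** The synopsis (Protocol 1.1) gives the primary symptom endpoint as "Improvement of patient comfort over the length of the study using a validated dry eye comfort questionnaire, OSDI". The Section 3 table says much the same and adds that both primary endpoints were validated in recent dry eye approvals. Section 9.1 refers to the OSDI scale, and Section 10.3 expands OSDI to ocular surface disease index. Section 9.4.2, however, describes the endpoint as the "dry eye comfort questionnaire OSDI defined as the mark listed in mm by the patient describing sensation of dryness".

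The only symptom procedure in the protocol is in Section 8.1. It is headed "Subject rated assessment of ocular discomfort by visual analog scale", yet the item asks about eye dryness at that moment, marked on a single 100 mm line.

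Eligibility mixes the terms as well. Inclusion criterion 6 reads "At least 40 mm on the ocular discomfort scale", while Section 5.3 allows rescreening of people who failed on their OSDI score.

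**Timing.** Section 8.1 opens its list with "Study assessments on each study day will occur in this order" and then says of the dryness line: "Subjects will be asked to subjectively rate their eye dryness at Visit 1,2, and 3". Section 9.4.2 says: "It will be measured at each study visit and reported as an ordinal endpoint". The schedule (Section 1.3) places Visit 3 on Day 14 and the final visit, Visit 13, on Day 84. Section 9.1 and the SAP both analyse the change from baseline to the final visit.

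**The concern.** One of the two primary endpoints has two identities. Someone reading Sections 1.1 and 3 expects a validated questionnaire. Someone carrying out Section 8.1 collects a one-item dryness rating. Reporting that rating as OSDI would put the wrong name on the result, and the validation statement in Section 3 cannot be tied to an instrument until one is named.

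The visit list raises a separate risk: the data may not exist. If the site works from the list in Section 8.1, participants who complete the study have no symptom score at the time point the primary analysis needs. If it works from Section 9.4.2, they have one. A primary endpoint should not depend on which sentence the site reads.

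**Working it through.** The documents state no effect size, standard deviation or power for this endpoint, so there is no design figure to reproduce. The check sets the sections side by side and does the visit arithmetic.

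**1. Which instrument?**

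| Section | Name used | mm scale? |
|---|---|---|
| 1.1, 3 | OSDI, a validated questionnaire | no |
| 5.1, criterion 6 | ocular discomfort scale | yes |
| 5.3 | OSDI score | no |
| 7.1 | subject-rated eye dryness | not stated |
| 8.1 | ocular discomfort in the heading, eye dryness in the item | yes, 100 mm |
| 9.1 | ocular discomfort on the OSDI scale | no |
| 9.4.2 | OSDI, defined as a mm dryness mark | yes |

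Apart from the abbreviation list, OSDI is used in 5 sections (1.1, 3, 5.3, 9.1, 9.4.2) and a mm scale in 3 (5.1, 8.1, 9.4.2). Section 9.4.2 uses both for the same endpoint. No section describes OSDI items, administration or scoring. The SAP names no instrument, so it cannot settle the question.

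**2. Which visits?** Section 1.3 shows four post-screening visits: Visit 1 (Day 1), Visit 2 (Day 7), Visit 3 (Day 14) and Visit 13 (Day 84).

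- Section 8.1 list: 3 of the 4 visits shown, the last on Day 14. Gap to the final visit: 84 - 14 = 70 days, or 10 weeks. The last listed rating falls 14/84 = 17% of the way to Day 84.
- Section 9.4.2: 4 of the 4 visits shown.

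**3. What is left for the analysis?** Section 9.2 plans 12 completers.

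- Baseline-to-final symptom pairs: 0 of 12 if the Section 8.1 list is followed, 12 of 12 if Section 9.4.2 is followed.
- Intervisit changes for the SAP: 3 - 1 = 2 under Section 8.1, and 4 - 1 = 3 under Section 9.4.2 for the visits shown.
- Assumption: if Visits 4 to 12 are weekly, which fits 7 x (13 - 1) = 84, Section 9.4.2 implies 13 ratings and 12 intervisit changes, against 3 ratings and 2 changes under Section 8.1.

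**4. Does anything else supply the Day 84 score?** Section 7.1 collects a dryness rating when study treatment is discontinued, which gives completers no Day 84 value. Section 9.4.2 says missing data will be imputed but gives no method, and if nobody is rated at Day 84 there is no observed final score on which to base one.

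**5. Screening and data type.** Criterion 6 needs a mm score, and Section 5.3 treats the symptom score as a reason for screen failure, yet the Section 8.1 list does not include screening. A lesser point: Section 9.4.2 calls the mm score ordinal, whereas Section 9.1 uses means and the SAP a t test.

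**The case against.** The strongest reply is that this is a labelling slip. Every operational section points to the mm dryness line, and OSDI is only a name with no rival procedure behind it. Read with the Section 9.4.2 definition, the 40 mm criterion and the OSDI score in Section 5.3 are the same measure. On timing, Section 8.1 never says that ratings stop at Visit 3. Its own lead-in covers every study day, and Sections 9.1 and 9.4.2 and the SAP all presuppose a final rating. The schedule also has a row whose label is missing from the text available, marked at screening, Day 1, Day 14 and Day 84. If that row is the symptom rating, the final score is already scheduled. Finally, this is an uncontrolled pilot that makes no claim to power.

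Part of this stands. The eligibility wording is a consequence of the same naming error and not a second defect. The loss of all Day 84 scores is a worst case that needs staff to follow one sentence against several others. A same-day Visit 1 rating could also serve criterion 6.

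The rest does not remove the problem. The synopsis and objectives still promise a questionnaire that nobody is told to administer. In Section 8.1 the general lead-in is followed directly by a visit list specific to this item, and a site could reasonably follow the specific instruction. The unlabelled row cannot be used either way. Even if it is the symptom rating, it omits Day 7, against both Sections 8.1 and 9.4.2, and includes Day 84, which Section 8.1 does not list. Power is beside the point, because even a descriptive mean change needs a defined instrument and a final measurement.

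**Conclusion.** The concern holds, and the text should be corrected before it is used. The protocol names the primary symptom endpoint as one instrument and defines it as another, and its sections give conflicting visit lists for it. The number of usable baseline-to-final symptom pairs runs from none to all 12 planned completers, depending on which section the site follows. The lower figure assumes that the Section 8.1 list is taken literally and that no other passage prompts a Day 84 rating; the upper figure assumes no missed ratings. The conclusion rests only on the documents' own wording and visit days. It does not rely on the unlabelled schedule row or on the weekly-visit assumption.

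**What to change.** The sponsor should name one primary symptom instrument and use it in Sections 1.1, 3, 5.1 (criterion 6), 5.3, 8.1, 9.1 and 9.4.2.

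- **Option A: the 0-100 mm eye-dryness scale.** This is the cheaper choice, because it alone has a written procedure and it matches the units of criterion 6. Remove the OSDI questionnaire from Sections 1.1 and 3, and replace OSDI in Sections 5.3, 9.1 and 9.4.2. Call the scale eye dryness, not ocular discomfort, in Sections 5.1, 8.1 and 9.1. Restate the Section 3 validation statement for this scale or delete it. Describe the score in Section 9.4.2 as continuous (0-100 mm).
- **Option B: the OSDI.** Add its administration and scoring to Section 8.1 and remove the mm definition from Section 9.4.2. State which instrument criterion 6 and the Section 5.3 rescreening rule refer to. If the dryness line is still collected, report it separately under its own name.

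Under either option, give one identical visit list in Sections 8.1 and 9.4.2 and in a labelled schedule row. It should include screening (for eligibility), Visit 1 (baseline) and Visit 13 (Day 84), and say whether the visits in between are included.

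The cost is protocol wording plus a rating at screening and at Visit 13, both of which already take place. Option B also needs the OSDI form and its scoring text.
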